## SCHEMA

### Dose Escalation Schema

Radiation Therapy	Dose Level	IV Cisplatin Weekly	PO Triapine*
Pelvic RT + Brachytherapy (+/- Extended)	-2	40 mg/m 	50 mg D1, 3, 5
	-1	40 mg/m 	50 mg QD x 5
	1	40 mg/m 	100 mg QD x 5
	2	40 mg/m 	150 mg QD x 5
	3	40 mg/m 	200 mg QD x 5

\*1 of the planned 25 doses of triapine will be delivered IV (day 1) at a fixed dose of 50 mg to allow PK and PD studies.

## 1. OBJECTIVES

### 1.1 Primary Objectives

- 1.1.1 To determine the Maximum Tolerable Dose (MTD) and Recommended Phase II Dose (RP2D) of oral triapine when used in combination with cisplatin plus radiation therapy.
- 1.1.2 To determine the oral bioavailability of triapine.
- 1.1.3 To describe the pharmacokinetics (PK) of oral and intravenous triapine.

### 1.2 Secondary Objectives

- 1.2.1 To determine whether the metabolic complete response (mCR) rate of oral triapine in combination with cisplatin chemoradiation using 18F-FDG-PET/CT at posttherapy (3-month) is at least 70%.
- 1.2.2 To determine clinical overall response rate, progression-free survival, and overall survival.
- 1.2.3 To determine the correlation of methemoglobin proportion (%) and triapine pharmacokinetic exposure.

### 1.3 Exploratory Endpoints

- 1.3.1 To determine whether active human immunodeficiency virus (HIV) antiretroviral therapy impacts the antitumor activity of triapine.

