3.1.3 ECOG performance status score of 0, 1, or 2. See [Appendix A](#)

3.1.4 Life expectancy greater than 6 months.

3.1.5 Normal organ and marrow function as defined below:

- Absolute neutrophil count (ANC)  $\geq 1.5 \times 10^9/L$
- Platelets  $\geq 100 \times 10^9/L$
- Hemoglobin (Hgb)  $\geq 10.0 \text{ g/dL}$  (blood transfusions to reach this amount are allowed)
- Serum creatinine  $\leq 1.5 \text{ mg/dL}$  to receive weekly cisplatin

If serum creatinine is between 1.5 and 1.9 mg/dL, patients are eligible for cisplatin if the estimated creatinine clearance (CCr) is  $> 30$  ml/min (for the purpose of estimating the CCr, the formula of Cockcroft and Gault for females should be used)

- Total serum bilirubin  $\leq 1.5 \times$  ULN (in patients with known Gilbert Syndrome, a total bilirubin  $\leq 3.0 \times$  ULN, with direct bilirubin  $\leq 1.5 \times$  ULN)
- AST and ALT  $\leq 2.5 \times$  ULN

3.1.6 Able to take oral medication.

3.1.7 Not pregnant and not breastfeeding. The effects of triapine on the developing human fetus are unknown. For this reason, as well as because heterocyclic carboxaldehydethiosemicarbazones and radiation are known to be teratogenic, women of child-bearing potential and men must agree to use two forms of contraception (hormonal or barrier method of birth control; abstinence) prior to study entry and for the duration of study participation. Patient must have documented negative urine pregnancy test must be resulted within 7 days before initiating protocol therapy. Should a woman become pregnant or suspect she is pregnant while participating in this study, she should inform her treating physician immediately. Because there is an unknown but potential risk for adverse events in nursing infants secondary to treatment of the mother with triapine, breastfeeding should be discontinued if the mother is treated with triapine. These potential risks may also apply to other agents used in this study.

3.1.8 For HIV and HEPB/C:

- HIV-infected patients on effective anti-retroviral therapy with undetectable viral load within 6 months are eligible for the dose escalation portion of this trial. For those patients who are enrolled in the HIV+ expansion cohort, they must be HIV infected and be on retroviral therapy with an undetectable viral load within 6 months of enrollment.
- For patients with evidence of chronic hepatitis B virus (HBV) infection, the HBV viral load must be undetectable on suppressive therapy, if indicated.

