### 5.1.3 Dose to be used for expansion

Dose escalation has been completed as of Amendment 10. The dose to be used for expansion is 100 mg triapine PO daily in combination with cisplatin based chemoradiation as described in this protocol. Data supporting this dose decision are detailed below and have been discussed with the CTEP Medical Monitor.

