##### **5.4.1 Expansion cohorts**

An expansion cohort will be treated at the MTD or the dose below that as stipulated above. Subjects will be enrolled into a non-HIV+ cohort (n=12) to further expand pharmacokinetic investigations and provide additional safety information or a 28-patient cohort of regionally advanced stage HIV+ uterine cervix cancer patients on active retroviral therapy. (Subject enrolled into this cohort may include such patients enrolled as part of the MTD determination.) Enrollment will not be time-limited but will be limited to patients with a

histologically confirmed diagnosis of locally advanced cervical or vaginal carcinoma not amenable to curative surgical resection alone to facilitate achievement of secondary objectives.

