13.1.1 The RP2D will be determined as described in section 5.1.2. Once the RP2D is determined, two expansion cohorts will be enrolled. Subjects will be enrolled into a non-HIV+ cohort (n=12) to further expand pharmacokinetic investigations and provide additional safety information. Additionally, up to 28 HIV+ cervical cancer patients (including the patients who were treated at the RP2D during the dose escalation stage) will be treated on RP2D to determine whether active HIV antiretroviral therapy impacts the antitumor activity of triapine. A Bayesian continuous monitoring will be used to ensure that the true DLT rate is controlled at 20%. To establish the stopping rule, a week prior distribution of DLT rate is set to be beta ( $\alpha=1, \beta=5$ ). If the posterior probability that the true underlying DLT rate exceeds 20% at RP2D is 70% or higher then the study accrual will be suspended and the toxicity data will be examined by the PI and the research team, who will subsequently decide on whether the trial should be terminated or not.

The enrollment suspension rule using the Bayesian analysis mentioned above can be represented as a table of possible outcomes for DLTs, as shown below.

Bayesian rule for suspending enrollment	
Suspend accrual if n patients experience a DLT	in N patients treated
2	3-4
3	5-8
4	9-13
5	14-17
6	18-22
7	23-26
8	27

The operating characteristics of this study design can be expressed in terms of probability of early suspending the enrollment at RD2P under the assumptions of various the true rates of DLT. The following table calculated these probabilities for a single dose level based on the simulation of 10,000 hypothetical trials.

Frequentist properties of Bayesian rule for suspending enrollment		
Probability of DLT	Probability of suspending	Median sample size for

	the enrollment	each dose level
0.1	0.10	28
0.17	0.32	28
0.2	0.45	28
0.25	0.66	13
0.3	0.83	8

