### 13.2 Sample Size/Accrual Rate

13.2.1 The number patients accrued to the study will depend on the MTD; an additional 12 cervical cancer patients may be treated at the RP2D to further define the spectrum of toxicities associated with the regimen and up to an additional 28 HIV+ patients will be enrolled to explore whether active (HIV) antiretroviral therapy impacts the antitumor activity of triapine. Although unlikely to happen, for the worst-case scenario, we could have needed  $6 \times 6 = 36$  patients for the phase dose escalation portion of the protocol, 12 for the non-HIV+ expansion cohort and none of the 6 patients on the MTD (or RP2D) is HIV+ cervical cancer patient. Thus, the maximum number of patients for this trial is  $36 + 12 + 28 = 76$ . Patients who do not complete at least 80% the first cycle of therapy and do not suffer a DLT which leads to the termination of the treatment during the observation period (5 weeks excluding treatment delay period) will not be evaluable and will be replaced. Review of patient toxicity and DLT monitoring will be conducted on a weekly basis by the PI and Phase I clinical team.

We expect that the accrual rate will be approximately 1 per 5 weeks. The follow-up period of the primary endpoint, DLT, is approximately 5 weeks after the starting of the treatment (excluding the treatment delay time as described in section 5.5). During the 3+3 dose escalation stage, we will allow the first 2 patients to be enrolled without stopping. During the expansion cohort, the patients will be accrued continuously. On the other hand, the treatment may be delayed during the DLT follow up period as described in section 5.5. Therefore, for a portion of the patients, the overall follow up time may be longer than 5 weeks. Thus, the accrual rate of 1 per 5 weeks is an estimate considering the facts stated above.

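### The exploratory objective on antiretroviral therapy asks for an effect the design cannot isolate: therapy is aliased with HIV status, and triapine with the chemoradiation backbone

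*Combined protocol and SAP*

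**What the plan says.** Section 1.3.1 sets the exploratory question of whether "antiretroviral therapy impacts the antitumor activity of triapine". Section 13.1.1 says that up to 28 HIV+ patients will be treated at the RP2D "to determine whether active HIV antiretroviral therapy impacts the antitumor activity of triapine". Section 13.2.1 repeats it in softer form: up to an additional "28 HIV+ patients will be enrolled to explore whether active (HIV) antiretroviral therapy impacts the antitumor activity of triapine".

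On who may enter, section 3.1.8 says of the HIV+ expansion cohort that "they must be HIV infected and be on retroviral therapy with an undetectable viral load within 6 months of enrollment". The same condition applies earlier in the trial: "HIV-infected patients on effective anti-retroviral therapy with undetectable viral load within 6 months are eligible for the dose escalation portion of this trial". Section 5.4.1 describes the group as a "28-patient cohort of regionally advanced stage HIV+ uterine cervix cancer patients on active retroviral therapy".

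On treatment, section 5.1.3 states: "The dose to be used for expansion is 100 mg triapine PO daily in combination with cisplatin based chemoradiation". There is no triapine-free arm and no randomization. The other expansion cohort is 12 non-HIV+ patients, enrolled for pharmacokinetics and additional safety information.

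On analysis, section 13.3.4 plans separate mCR and objective response proportions in the HIV+ and non-HIV+ cohorts, each with an exact 95% interval. It calls the objective exploratory and says the trial is not powered for formal tests between the cohorts. Section 13.3.5 plans no comparison of triapine pharmacokinetics by antiretroviral therapy.

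**The concern.** An effect of antiretroviral therapy on triapine's antitumor activity is an interaction. It asks whether the benefit that triapine adds to chemoradiation differs with and without antiretroviral therapy in comparable patients. To estimate it, both antiretroviral therapy and triapine have to vary. In this trial neither varies independently: therapy changes only when HIV status changes, and triapine does not change at all.

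The question is the stated purpose of the larger of the two expansion cohorts, and two of the three statements of it promise a determination. At stake is what the trial may conclude. The planned estimates can describe response in HIV+ patients on therapy, but they cannot answer the question as worded.

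**Working it through.** **Inputs.** Antiretroviral therapy (ART) status by eligibility: 3.1.8 and 5.4.1. Triapine for all: 5.1.3. Cohort sizes of 28 and 12: 5.4.1 and 13.1.1. Reference mCR of about 70% after cisplatin chemoradiation: 2.4.2. Response above 90% with IV triapine: 13.3.4. Rule of 23 of 28 with a 5-point margin and 5% type I error: 13.3.4.

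**Step 1: the plan's own figures for 28 patients.** No figure is given for the ART objective. The number 28 appears elsewhere and reproduces:

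- mCR rule: the null is 0.70 − 0.05 = 0.65. By exact binomial with n = 28, one-sided, P(X ≥ 22) = 0.092 and P(X ≥ 23) = 0.039, so 23 is the smallest cutoff within 5%.
- Bioavailability: 0.67 × 10^(±1.96 × 0.175/√28) = 0.58 to 0.78, inside the stated 0.53 to 0.83.

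**Step 2: which combinations occur.**

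| HIV | ART | Triapine | Patients in the trial |
|---|---|---|---|
| yes | yes | yes | up to 28 |
| no | no | yes | 12 in expansion |
| yes | no | yes | none (3.1.8) |
| yes | yes | no | none (5.1.3) |
| yes | no | no | none |

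HIV+ patients from dose escalation fall in the first row too, because the same ART condition applied to them.

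**Step 3: target against what can be observed.** Write p(h, a, t) for the mCR rate by HIV status, ART and triapine.

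- Target: Δ = [p(1,1,1) − p(1,1,0)] − [p(1,0,1) − p(1,0,0)]. Three of its four terms belong to empty rows.
- Observable: D = p(1,1,1) − p(0,0,1).
- Adding and subtracting terms: D = Δ + [p(1,1,0) − p(1,0,0)] + [p(1,0,1) − p(0,0,1)].

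The second term is any effect of ART on response to the chemoradiation backbone. The third is any effect of HIV infection itself. Case-mix differences between non-randomized cohorts add to these. Suppose mCR were 70% in the HIV+ cohort and 90% in the non-HIV+ cohort, so D = −20 points. The data would fit Δ = −20 with the other terms zero just as well as Δ = 0 with an HIV effect of −20. Nothing within these two cells distinguishes them, at any sample size.

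The literature value of about 70% in 2.4.2 does not fill the gap, since the protocol does not give it by HIV or ART status.

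**Step 4: precision of D, as a side check.** The 95% half-width is approximately 1.96 × √[p(1−p)(1/28 + 1/n₂)], a rough approximation at n₂ = 12.

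| Common mCR | n₂ = 12 | n₂ = 18 |
|---|---|---|
| 70% | 31 points | 27 points |
| 90% | 20 points | 18 points |

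The column for 18 assumes that the six evaluable patients treated at 100 mg in escalation are added and that all are non-HIV+, which the documents do not state. For 70% against 90% at two-sided 5%, power is 23% (normal approximation) or 15% (exact Fisher) with 12 comparators, and 34% or 27% with 18. This is the limitation that 13.3.4 already admits. It is separate from Step 3.

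**The case against.** The best defense is that the objective is labeled exploratory, that 13.3.4 plans only separate proportions with exact intervals, and that the lack of power is disclosed. That largely stands, and it limits the weight of the point. A reader might infer that any cohort difference, or similarity, will be reported as an antiretroviral effect. The documents do not say so: there is no between-cohort test, decision rule or attribution step. What the disclaimer leaves out is the confounding. A statement about power alone suggests that a larger trial of the same design would settle the question, which Step 3 shows it would not.

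A reader might also infer that no analysis of these data could bear on antiretroviral therapy at all. That goes too far. If regimens differ among the HIV+ patients, response or exposure could be described by regimen, although weakly and without randomization. What is out of reach is therapy versus no therapy, and triapine apart from its backbone.

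Finally, a reader might infer that the cohort of 28 loses its justification. It does not. Twenty-eight patients at the RP2D also underlie the bioavailability precision statement (13.1, 13.3.5) and the 23-of-28 mCR rule (13.3.4), and patients at the RP2D are subject to the DLT monitoring in 13.1.1.

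**Conclusion.** The point holds for the objective as worded. Antiretroviral therapy is fully aliased with HIV status, and triapine's activity cannot be separated from cisplatin chemoradiation. Sections 1.3.1, 13.1.1 and 13.2.1 therefore state an inference that the design cannot deliver. This is a matter of identification, so it does not depend on the precision figures in Step 4, which rest on assumed response rates and comparator sizes.

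The conclusion assumes that the eligibility rule in 3.1.8 is followed, that non-HIV+ patients are not taking antiretroviral therapy, and that no outside comparison group is intended, since none is described.

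The consequence is contained. It affects one exploratory objective and leaves the primary and secondary analyses, the monitoring rule and the sample size as they are.

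**What to change.** 1. In 1.3.1, 13.1.1 and 13.2.1, replace the objective with: *to estimate the mCR rate, objective response rate, DLT rate and triapine PK in HIV+ patients on suppressive antiretroviral therapy treated at the RP2D.*
2. In 13.3.4, add: *Differences between the HIV+ and non-HIV+ cohorts will not be attributed to antiretroviral therapy or to an effect on triapine.*
3. Optionally, in 13.3.5, add a descriptive comparison of triapine AUC by recorded antiretroviral regimen within the HIV+ cohort, labeled as addressing exposure and not antitumor activity. The inputs are already collected: section 5.6 requires all concurrent drugs to be recorded, and sections 9.1.1 and 10 schedule the PK sampling. Section 8.1 gives a reason to look, since it reports that triapine is metabolized by CYP450 enzymes, mainly CYP1A2.

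The cost is a more modest exploratory claim, three wording edits, one added sentence and, if item 3 is taken up, a small descriptive table. Item 1 also means reporting DLT rate and PK for the HIV+ cohort separately, a split that 13.3.3 and 13.3.5 do not now specify. Eligibility, treatment and sample size are unchanged.

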## 2. BACKGROUND

### 2.1 Locally Advanced Cervical Cancer (LACC)

In the United States, cervical cancer is the third most common gynecologic cancer with approximately 12,000 new cases and 4,000 succumbing to disease per year. There is no curative surgical option for this patient cohort, and since 1999, concurrent chemoradiation with cisplatin 40 mg/m^2 weekly has been widely adopted as standard of care for this cohort of patients. While the majority of women are diagnosed with early-stage disease, women with locally advanced cervical cancer (LACC, stage IB2 to IVA) have a 5-year survival rate ranging from 80% (stage IB) to 30% (stage III), and it is this subgroup that accounts for the large majority of deaths associated with cervical cancer. As a result, there remains an urgent need to identify novel agents and/or combination regimens to improve overall survival in patients with locally advanced cervical cancer.

—

## 2.2 CTEP Agent: Triapine

### 2.2.1 IV Triapine

NCI-CTEP has supported a phase I trial (NCI 7336, clinicaltrials.gov NCT00335998) and a phase II trial (NCI 8327, clinicaltrials.gov NCT00941070) evaluating the safety and clinical efficacy of intravenous triapine combined with cisplatin chemoradiation for the management of IB2-IVA cancer of the uterine cervix. Triapine is a 500-to-1000-fold more potent inhibitor of ribonucleotide reductase (RNR) M2 and M2b than hydroxyurea, which has previously shown clinical activity in cervical cancer. The half-life of triapine is approximately 2 hours, suggesting that repeat dosing is needed within one treatment week to optimize clinical efficacy. Cervical cancer cells treated at human pharmacokinetic (PK) concentrations and exposure times survive at a rate of 80% after triapine alone, 40% after triapine plus cisplatin, and 10% after 3-AP plus cisplatin plus radiation. In phase I and II trials, intravenous triapine (25 mg/m^2) was given three times weekly co-administered with weekly cisplatin (40 mg/m^2) and daily radiation (50.4 Gy in 28 fractions) plus brachytherapy (35-40 Gy) in 35 patients with advanced stage cervical and vaginal cancer. This regimen was well-tolerated as a total of 500 (95%) of 525 2-hour 3-AP infusions were administered with the most common side effects being grade 2 diarrhea, grade 2 electrolyte imbalance, grade 2 fatigue, and infrequent grade 3 pancytopenia. In the IV trial (NSC 3663249), 90% of toxicity for this combined regimen occurred within the first 5 weeks of treatment, there is no currently known cumulative risk of toxicity associated with triapine ([name], personal communication). With respect to the secondary objectives of this trial, 3-month metabolic complete responses (mCRs), as determined by PET-CT, were observed in 23 (96%) of 24 patients in whom images were obtained in the phase II study. To date, 29 of 35 (86%) locally advanced cervical cancer patients are alive and disease-free at a median follow-up of 24 months. Four of 35 (11%) patients have died from extra-pelvic disease progression. Based on these findings, a randomized phase II trial of IV triapine in combination with concurrent cisplatin and radiation therapy was initiated (clinicaltrials.gov NCT01835171; Target accrual 188; opened 01/15/2016).

### 2.2.2 Oral Triapine

While the clinical activity of IV triapine in combination with standard chemoradiation therapy appears to be promising, it is quite time-intensive to perform a 2-hour infusion 3 times a week. Additionally, the PK data from IV triapine indicated that peak serum concentrations occur 1-2 hours after a 2-hour infusion, suggesting only a potential transient therapeutic benefit. It is conceivable, therefore, that daily dosing of triapine may yield greater clinical benefit. Recently, a phase I trial evaluated single-agent oral triapine in patients with a wide range of advanced solid tumors, enrolling 20 patients, including 1 woman with cervical cancer. Treatment consisted of oral triapine administered every 12 hours for 5 consecutive doses on days 1-3, 8-10, and 15-17 of an every 28-day cycle. Triapine was initially dosed at 50 mg every 12 hours and then increased to dose levels of 100, 150, and 200 mg every 12 hours. On this trial, grade 3/4 adverse events were uncommon at the 50 mg (1 hypertensive episode) and at the 100 mg (1 anemia) dose levels. Three patients experienced (38%) grade 3 or 4 neutropenia at the 150 mg dose level. At the 200 mg dose level, two grade 3-4 hypoxia events and grade 3-4 anemia, neutropenia,

thrombocytopenia, infection, fatigue, hepatic enzyme elevation, and anorexia adverse events were observed rarely. The recommended phase II dose was 150 mg every 12 hours for five consecutive doses on days 1–3, 8–10, and 15–17 of each 28-day cycle. Ultimately, 8 patients were treated at the 150 mg dose level with 1 DLT observed. Pharmacokinetic (PK) analysis suggested that the 150 mg dose achieved a minimum inhibitory concentration of RNR for six hours, which is similar to what is observed with IV dosing. In addition, the PK data suggested that the population average bioavailability of triapine was approximately 55-70%.

### **2.3 Rationale for the combination of triapine with concurrent chemoradiation**

Ribonucleotide reductase (RNR) is the rate-limiting enzyme in the synthesis and repair of DNA, and it is directly involved in the cellular response to radiation, making RNR-targeted therapy to enhance radiation treatment a rational therapeutic strategy. Inhibition of this pathway may be both radiosensitizing and chemosensitizing, thereby making investigation of combination therapy with chemoradiation a promising therapeutic strategy. There is an unmet therapeutic need to improve complete metabolic response during definitive chemoradiation in patients with locally advanced disease who are at high risk for recurrence.

RNR is the only enzyme responsible for conversion of ribonucleoside diphosphate to deoxyribonucleotide diphosphate (dNDP), the key building blocks for DNA synthesis. RNR is composed of a heterodimeric tetramer comprised of two dimers M1·M2 or M1·M2b. When RNR is inhibited, the supply of dNDPs and dNTPs is reduced. Inhibition of key nucleotide precursors for DNA biosynthesis results in a protracted repair of damaged DNA, which in turn, enhances the potential cytotoxic effects of chemotherapy and radiation therapy. Cervical cancer preferentially overexpresses the RNR M2b and M2 subunits, and this overexpression is associated with resistance to cisplatin-based chemoradiotherapy. As such, RNR inhibitors have been developed as potential radiation sensitizers over the past 30 years. While the initial data was promising, the older inhibitor compounds had displayed mixed clinical effectiveness, and they were associated with significant toxicity. However, there was sufficient proof of concept to suggest that a RNR inhibitor may be efficacious when used in combined modality therapy. Newer RNR inhibitors have increased potency and improved binding characteristics, which has significantly renewed interest in their clinical development. The RNR inhibitor 3-aminopyridine-2- carboxaldehyde-thiosemicarbazone (3-AP, triapine, NSC#663249) was developed by the Sartorelli laboratory at the Yale Cancer Center, and extensive pre-clinical studies have shown it this agent to be an equipotent inhibitor of M2b and M2.

